## **RECRUITMENT PROCEDURES**

Participants are recruited through online recruitment on both social networking sites and alcohol screening sites. If a participant is interested they create an anonymous unique code and complete a brief survey online and if they are eligible they are instructed to call the researcher at a time that fits their schedule.

## **INFORMED CONSENT**

Electronic consent will be obtained after the phone call and the initial screening procedures and verbal consent will be obtained via the RA during the phone screening process. However, all participants will have a version of the consent to review prior to the phone call to ensure that they have the opportunity to understand the study in advance of the phone call. Electronic signatures or initials for consent are used in many types of legal, financial and healthcare settings. An electronic signature for the purpose of US law as "an electronic sound, symbol, or process, attached to or logically associated with a contract or other record and executed or adopted by a person with the intent to sign the record. For the purposes of this study, potential participants will both need to agree to the consent form, write in their initials, pass the consent form quiz, and give verbal assent to complete the consent process and be enrolled. If eligible based on the web and phone screening, participants will be given an online consent form to complete and sign. The research team will be responsible for obtaining from every participant prior to his/her participation in the study an informed consent signed by the participant with their initials AND assent on the phone, in accordance with the CFR, Title 45 Part 46. Consent will be obtained from the participant after a full explanation of the purpose of the study, risks and discomforts involved, potential benefits, etc. have been provided by the Investigator both verbally and in writing. Informed consent will be obtained by study staff on the phone. Once the

consent is completed, the RA will review the consent form quiz and call the participant to discuss any wrong answers or additional questions about the study.

### **DISCOMFORTS AND RISKS**

There is some risk that participants will be identified as participants in a study of treatment for problem drinking via participant contact or through the mobile phone message or that the self-report assessments will adversely affect participants' well-being. Computerized assessment and messaging. The primary concern to confidentiality is that there may be an inadvertent breach of confidentiality concerning problem drinking behavior. It is possible that since participants will be receiving messages on their personal mobile phones, another person may view a message specific to changing alcohol use from an unguarded phone. While unlikely, it is possible that there may be a breach of confidentiality if a participant's home number is obtained through the computer database. Like all studies, individuals will be assigned to the assessment only group. However, they will receive guidelines on safe drinking. Rating scales and questionnaires Assessments are all non-invasive and add no special risk, although they do cover sensitive areas. The major disadvantages are the time taken to complete them, and possible breach of confidentiality. Our past experience indicates that these measures are acceptable to participants. Careful efforts to maintain confidentiality have been effective in our previous research and will be continued.

Participants will be recruited through the internet and before any messages are sent will be contacted by a research assistant to review the consent form – including an explanation of the study protocol, its risks, potential benefits, and alternative treatment. Additionally, all participants must complete the consent form quiz to ensure comprehension. An entire copy of the informed consent form will be available for download by the participant. Protection against risk - Inclusion criteria and the use of trained research staff following the initial screening will minimize acceptance of participants with severe alcohol use disorders into the study. Participants with a history or current symptoms of alcohol withdrawal will be referred to more intensive care. During the intervention phase, participants' alcohol use will be monitored through EMA. If a participant reports drinking at greater level, the RA will call the participant. Participants will be given the emergency numbers of the PI and study RA for consultation. Participants who have dropped out of study treatment and are interested in returning to the program or attending another program will be referred for appropriate treatment according to their needs and wishes. We will not be asking individuals sensitive information about harm to self until we have contact information so we can contact them. Numerous studies have been conducted over the internet and mobile phones without any subject contact. There have been more internet based intervention studies for alcohol use than any other disorder. We have significantly

more information that most studies in that we will have actual contact with the individuals in the study by telephone prior to the study beginning then again at week 4 and week 12. Regular SMS reminders will be sent to individuals enrolled in all arms of the study to remind them 1) if they want standard treatment, they can call the RA and be helped with referrals and 2) if they are worsening clinically, they can call for help. If a participant is threatening to harm themselves or another we will use standard protocol to inform the proper authorities as if it was a patient through phone contact as we will have their address and phone number. This will be determined based on email, phone, mobile or web-based data from the participant. We have had no adverse events with the first 104 individuals enrolled.

### **POTENTIAL BENEFITS**

Benefits to participants include additional monitoring and reminders to help them reduce their drinking. Based on the efficacy of previous messaging interventions for smoking cessation, it is possible that participants reduce the personal and public consequences associated with problem drinking. We expect that the brief feedback and EMA only group may also find benefit in the extra monitoring. Moreover, all participants have their choice of messages for 12 weeks after the study period. If the intervention is found to be useful to participants, it will provide a minimal resource automated intervention for those seeking to reduce their drinking.

### **DISCONTINUATION OF STUDY/SUBJECT WITHDRAWAL**

If a participant self-reports worsening of their condition as a result of the study procedures they will be withdrawn. All participants data will be reviewed at week 4. For those who report their condition has gotten worse, we will call them and inquire about their current symptoms and discontinue them from the study if necessary. Participants can withdraw at any time and we provide referrals. We provide referrals to internet screening sites and treatment using the SAMHSA Treatment finder. We inquire about reasons for withdrawing.

### **ADVERSE EVENTS**

The Principal Investigator and Co-Investigators are clinical psychologists and licensed Ph.D. social workers and will be responsible for distinguishing between a Serious Adverse Event (SAE) and a non-serious adverse event (AE). All SAE and AE will be reported to the IRB of the NSLIJ according to NSLIJ HRPP policies and to the National Institute of Alcohol Abuse and Alcoholism (NIAAA) project officer within 48 hours of its occurrence. Additionally, the PI will prepare an annual report summarizing all SAE and AE to be submitted to the NIAAA project officer and the IRB. In addition to preparing for SAE, participants' alcohol use will be monitored. Participants will be referred for appropriate treatment according to their needs and wishes if they show severe deterioration, and continued evaluation of participants through assessments will provide ongoing information concerning their clinical status. Significant deterioration is

defined as a significant increase in drinking since the baseline interview; or other indicators through any interaction with the research staff. If any of these indicators are present, the participants will be immediately withdrawn from the study and referred to immediate and appropriate treatment. Primary responsibility and decision making in regards to participants remaining in or being withdrawn from the study will lie with the principal investigator.

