This study is now in the recruitment phase. We have already developed all messaging groups and done preliminary research on user preferences with 50 problem drinkers and 400 individuals on messaging preferences. This IRB protocol is only for the actual testing of the different forms of messaging in 240 individuals. The primary intervention group is the adaptive tailored group which includes messages tailored to a baseline survey results (including drinking times) and adaptive to ongoing drinking patterns and goal achievement via interactive ecological momentary assessment (EMA) which is real-time assessment and responses that are tailored to the persons current functioning. Other features include participant initiated help messaging and support network (e.g. spouse) alerts. We are testing the intervention with 240 PDs over a 12-week period. We are comparing 5 types of messaging: 1) tailored content and timed messaging adaptive to the participants current state (Beta Intervention); 2) Tailored content messaging (not adaptive or timed) sent at 6pm every day; 3) untailored consequence based messages sent at 6pm every day; 4) untailored benefit based messaging sent at 6pm every day and 5) Brief feedback and EMA only. In addition, we have a "goal only" group that does not mention alcohol. Web-based assessments will be completed at screening, baseline, at week 4, week 12 and through weekly EMA via SMS. All individuals are offered an additional 12 weeks of messaging in the group of their choice.

Description of Procedures:

**Please note: This study is done completely over the web and phone. There are no office visits at all. It is all distant virtual interaction.**

A brief bullet point review of general procedures is below:

- Recruit problem drinkers online
- Screen potential participants online
- Create phone screening appointment
- Offer consent form for review prior to call
- Screen participant on the telephone
- Obtain consent on the phone (participant completes after eligibility and it will be reviewed by staff prior to enrollment).

- Explain procedures (12 week study)
- Guide individual to complete baseline assessment
- Randomize participant
- Sign each individual participant up for the messaging program
- Review how to respond to assessment messages.
- Review procedures based on group assignment (What to Expect)
- Provide contact information of the RA & PI
- Email participants at week 4 to ensure safety and concerns (Week 4 Survey)

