**Follow-up Assessment:** We will conduct a brief web-based week 4 assessment to assess drinking variables and overall functioning. This is 15-20 questions. Three days before their 12-week completion date participants will be sent a reminder text and email to complete the final assessment via a web-based survey. The week 12 assessment will include all the baseline measures as well as an item on perceived relevance of the intervention content to them specifically (Strecher, Shiffman, & West, 2006), treatment history during the intervention, overall recommendations to improve the intervention in addition to additional resources for PD. During the course of the study, additional data elements such as the number of eligible vs. ineligible participants, reasons for exclusion, referral sites, length of time to complete the screening and each assessment, and numbers of persons who drop out at any point in the study and at which point they drop out.

**Ecological Assessment:** Once the study begins all subjects will receive weekly ecological assessment for assessment only purposes (TA arm will also receive interactive assessment). **Weekly Drinking:** Three items will be sent every seven days including: The number of drinking days in the last week, the average number of drinks per drinking day in the last week, and number of drinking days where more than 5 drinks were consumed (4 for women) in the last week. We will also ask about

improvement over the course of the week to both assess change but also guide the adaptive intervention group. We chose this time to send messages during the day to reduce the chances that individuals will be intoxicated while reporting their drinking in their natural environment. Shiffman (2009) highlights the use of EMA to collect data from drinking and substance abusing populations and highlights while some have shown mild intervention effects (e.g. Collins et al., 1998) that most show little reactivity. Moreover, collecting weekly drinking assessments should reduce the likelihood of reactivity.

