**Measures & Schedule of Events (See Attached)**

Measure	Construct	Time					Optional Messaging
		Screen	Intervention Messaging Period			Weeks 12-24	
			Baseline (Randomize)	Weekly EMA	Week 4	Week 12	
Demographics	-	X	X			X	
QFV-30 questionnaire*	Alcohol consumptions last 30 days	X			X		
QFV-90 questionnaire*	Alcohol consumptions last 90 days		X			X	
EMA (Drinking Days, Drinks per Drinking Day, Heavy Drinking Days)	Weekly alcohol consumption			X			X
Frequency of Drug Use	Frequency drug use last 30 days	X				X	
Tx History & Medications	Substance abuse and mental health treatment history (last year) and current medications.	X				X	
Short Alcohol Withdrawal Scale*	Alcohol withdrawal potential	X					
Short Inventory of Problems*	Alcohol related consequences		X			X	
3-Item Primary Appraisal Measure: Alcohol	Subjective harm from use, continued use and benefit to stopping		X		X	X	
The Obsessive-Compulsive Drinking Scale*	Craving, salience and loss of control over alcohol		X			X	
Drinking Norms Rating Form	Perceptions of participants own and others drinking behavior		X			X	
Drinking Goals	Daily and weekly consumption goals	X	X		X	X	
Typical Drinking Patterns	When individuals are most likely to drink heavily		X		X	X	
Goal Commitment	Commitment to moderation and individual goals		X	X	X	X	
Single item rulers	Readiness to change, importance, and confidence to change.		X		X	X	
Triggers Questionnaire	Situations that may trigger heavy drinking		X			X	
Relevance of intervention to needs	Single item on whether material was relevant to participant				X	X	

Other sources of help sought	Outside help sought during the intervention					X	
Satisfaction and recommendations	Overall program satisfaction and recommendations.					X	

\*Validated scales

A brief description of the site(s) where the research is to be conducted, including information about the adequacy of facilities for the safe and appropriate conduct of the research, and relevant demographic and epidemiological information about the country of region concerned.

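### The 48-hour adverse-event clock starts at occurrence, but no scheduled measure is described as an adverse-event inquiry, so the rule cannot be reliably met and 0 of 104 is weak evidence

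*Protocol*

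**What the plan says.** **Reporting rule.** Under Adverse Events, "All SAE and AE will be reported to the IRB of the NSLIJ according to NSLIJ HRPP policies", and they also go to the NIAAA "project officer within 48 hours of its occurrence". The clock starts at the event and covers non-serious as well as serious events.

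**Setting.** Under Experimental Design: "There are no office visits at all. It is all distant virtual interaction".

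**Schedule.** The table under Measures & Schedule of Events has no row for adverse events. SAWS, labelled "Alcohol withdrawal potential", is marked at screening only. The week 12 survey repeats the baseline measures, and SAWS is not one of them.

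**Safety contacts that the text describes.**
- A step in the procedures list: "Email participants at week 4 to ensure safety and concerns (Week 4 Survey".
- A "brief web-based week 4 assessment to assess drinking variables and overall functioning" (Follow-up Assessment).
- Review of all participants' week 4 data. For those who report worsening, "we will call them and inquire about their current symptoms" (Discontinuation of Study/Subject Withdrawal).
- Telephone contact at weeks 4 and 12, a call from the research assistant when reported drinking is higher, and text reminders in all arms that a participant who is getting worse can call (Discomforts and Risks).
- At week 12, items on treatment history and medications, alcohol-related problems and outside help sought (schedule table).

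**Interim statement.** Under Discomforts and Risks: "We have had no adverse events with the first 104 individuals enrolled".

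**The concern.** With no visits, staff learn of an event only when the participant reports it or when a contact happens to reveal it. A deadline counted from occurrence can pass before anyone in the study knows of the event. The promise made to the funder then depends on how often, and how directly, participants are asked.

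The named drinking triggers also point one way. The Adverse Events section defines deterioration by increased drinking, and the research assistant's call is for higher drinking. The intervention aims at less drinking, and withdrawal is a risk that the protocol screens for. A participant who cuts down and develops symptoms would not trip either drinking trigger. What remains is self-reported worsening and a general clause on other signs noticed by staff.

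Two things are at stake: keeping the reporting commitment, and how much weight the Data and Safety Monitoring Board (DSMB) can put on a low count when it judges risk against benefit.

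**Working it through.** There is no design figure to reproduce; 0/104 is an observed count. Two checks show what the text implies.

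**1. Share of events that could be known within 48 hours.**

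Inputs: 48 hours = 2 days (Adverse Events); a 12-week period = 84 days, with contacts at weeks 4 and 12 and weekly drinking reports by text (Experimental Design). Assumptions: an event is equally likely on any day, and it is learned of only at the next scheduled contact. The share in time is then 2 days divided by the gap between contacts.

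- Baseline to week 4: 2/28 = 7.1%.
- Week 4 to week 12: 2/56 = 3.6%.
- Whole period, contacts at weeks 4 and 12 only: (2 + 2)/84 = 4.8%.
- If the weekly drinking report also revealed events: 2/7 = 28.6%. This is hypothetical, because the weekly items as described cover drinking, commitment and improvement.

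These shares apply to events that surface only at a contact. An event that a participant phones in promptly can meet the deadline.

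**2. What 0 of 104 can exclude.**

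The exact one-sided 95% upper limit for zero events in n people is 1 − 0.05^(1/n). With n = 104 this is 1 − 0.05^(1/104) = 2.84%. If only a fraction c of events is captured, the limit applies to the recorded rate, and the limit on the true rate is 2.84%/c. The protocol gives no value for c, so the range below is assumed. The last column is (1 − 0.05c)^104.

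| Capture c (assumed) | Upper limit on true rate | Chance of 0 recorded if the true rate is 5% |
|---|---|---|
| 100% | 2.8% | 0.5% |
| 50% | 5.7% | 7% |
| 25% | 11.4% | 27% |

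With full capture, a zero count would be strong evidence against a 5% rate. At one quarter capture it would occur about one time in four.

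**3. The week 4 contact across sections.** It is an email in the procedures list, a web survey under Follow-up Assessment, a telephone contact under Discomforts and Risks, and a call only to those reporting worsening under Discontinuation. An email could carry the link to the survey. A telephone contact described without restriction and a call limited to those who report worsening are not the same procedure.

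**The case against.** The strongest reply is that the protocol does look for safety problems. It has a week 4 contact with a stated safety purpose, a staff-initiated symptom call, calls triggered by higher drinking, reminders in every arm, and week 12 items on treatment, problems and help sought. The definition of deterioration extends to any other sign noticed by staff. The entry criteria screen for withdrawal, and those with symptoms or a history of it are referred elsewhere. The forms are attached but not shown and may hold an AE question.

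Much of this stands, and it rules out several readings that a reader might infer:

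- *That the deadline can never be met.* Events volunteered promptly can comply, and the documents give no rate of volunteering. They therefore do not show that most events will be late.
- *That events surface only if volunteered, or that a symptomatic participant looks well on every measure.* The symptom call, the functioning questions and the week 12 items contradict this.
- *That no form asks about adverse events.* This cannot be shown without the forms.
- *That the adaptive arm will record more events because it has more interaction.* This is plausible, but nothing in the text says that its automated exchanges pass events to staff, and the reminders go to all arms.

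The reply does not remove the point. The symptom call reaches only those who already report worsening, the reminders invite a call rather than ask a question, and the week 12 treatment item concerns substance-use and mental-health care and medications. None is described as an AE inquiry. Even if the forms hold one, an event first learned of at week 4 or week 12 is usually past 48 hours, so the problem with the clock remains.

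**Conclusion.** The concern holds in a limited form. Counting 48 hours from occurrence, for every AE, cannot be reliably met in a remote trial for events first learned of at a scheduled contact. About 5% of such events would be in time with contacts at weeks 4 and 12 only, given even event times. The text shown describes no structured AE inquiry and no repeat of SAWS after screening.

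The zero count is weak evidence rather than no evidence. Its upper limit is 2.8% with full capture and about 5.7% if half of events are captured, the half being an assumption. The protocol does not say how events were sought among the 104, or how long they had been followed. To call the count uninformative would go too far: it bounds the rate for any stated level of capture.

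This affects safety ascertainment and a reporting commitment, not the efficacy analysis. It is worth correcting because the remedy is cheap and goes beyond added detail.

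**What to change.** - Start the 48-hour clock at the study staff's first awareness of the event.
- Unless the attached forms already contain it, add one identical AE item to the existing week 4 and week 12 web surveys in all arms, and repeat the existing SAWS in those surveys.
- Give the DSMB counts by arm, with solicited and volunteered events separated.
- Beside the 0 of 104 statement, say how events were ascertained.
- Reconcile Experimental Design (procedures list and Follow-up Assessment), the schedule table, Discomforts and Risks, Discontinuation and Adverse Events on how and when events are sought, including the form of the week 4 contact. What clinical action follows a positive answer is for the sponsor to settle.

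The cost is protocol wording and a few more questions, which will be felt most on a week 4 survey of 15 to 20 items. More minor AEs will be reported.

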### **DATA SAFETY MONITORING**

The protocol has been reviewed by study staff, external consultants and the IRB. In addition, an independent Data and Safety Monitoring Board (DSMB) has been formed. No members are otherwise affiliated with the study. Each of the DSMB members have had extensive clinical and/or research experience with the study population. The members of the board include the following:

- [name]., Assistant Clinical Professor of Psychiatry, Columbia University College of Physicians and Surgeons.
- [name]., Associate Director of Health Services Research, National Center on Addiction and Substance Abuse at Columbia University.

The DSMB shall determine safe and effective conduct and recommend conclusion of a trial if significant risks develop or the trial is unlikely to be concluded successfully. Specifically, the data and safety monitoring board and PI shall be responsible for the following:

- Data monitoring that will take place on a regular basis (every 6 months after recruitment or the halfway point of the trial).
- Evaluating the progress of the trial, participant risk versus benefit, and other factors that may affect study outcome. Monitoring may also consider factors external to the study when interpreting the data, such as scientific or therapeutic developments that may have an impact on the safety of the participants or ethical issues related to the study.
- Inquiring for further information as necessary to accomplish their mission.
- Maintaining confidentiality during all phases of the trial including the monitoring, preparation of interim results, review and response to monitoring recommendations.

